**Table 2: Analysis Windows**

Analysis label	Visit	Target Day	Interval Lower Bound	Interval Upper Bound
Vital signs, Clinical Laboratory tests				
Baseline*		1	-INF	1
Week 2		15	2	22
Week 4		29	23	43
Week 8		57	44	85
Week 16		113	86	141
Week 24		169	142	197
Week 28		198	198	+INF
12-Lead ECG				
Baseline*		1	-INF	1
Day 1		1	1	2
Week 2		15	3	64
Week 16		113	65	141
Week 24		169	142	197
Week 28		198	198	+INF
mRSS				
Baseline*		1	-INF	1
Week 4		29	2	43
Week 8		57	44	85
Week 16		113	86	141
Week 24		169	142	197
Week 28		198	198	+INF

---

IMP administration. If no triplicate (or duplicate) results are available before the first dose, the last value before first study drug administration will be used.

### **Selection of Visits**

Per parameter, analysis visit and timepoint, the value closest to the target date will be used in analysis tables and figures. Other values will be listed only. If more than one value is located at the same distance from the target day, then the latest in time will be selected. If there are two values on the same day and no time indicating which one is last, the average of the two will be calculated.

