### **4.5.4. Treatment Discontinuation (Temporarily and Permanently), Subject Withdrawal, and Study Termination**

A subject may be withdrawn from the clinical study at any time without the subject's consent if the investigator or sponsor determines that it is not in the best interest of the subject to continue participation. In such case, the reason for withdrawal will be documented in the source documents, and the subject will complete the ED visit and follow-up visits for safety assessments.

Treatment with IMP should be discontinued by the investigator (preferably after discussion with the CRO medical monitor, who may consult and must inform the sponsor's study physician) for any of the following conditions:

- Life-threatening AE or an SAE that places the subject at immediate risk.
- Serious infections deemed related to study treatment by the investigator, and requiring parenteral antimicrobial therapy and/or hospitalization.
- Confirmed pregnancy: if a subject becomes pregnant during the study (to be confirmed by local serum pregnancy test; central measurement will also be performed), the IMP has to be stopped immediately and the subject has to be followed up until birth or otherwise termination of pregnancy. The subject needs to be unblinded immediately and repeat counseling on birth defect risk must be offered in case she was on active drug.
- Arrhythmia or conduction abnormality, including but not limited to prolonged QTcF, where the severity is categorized as Common Terminology Criteria for Adverse Events (CTCAE) Grade 3 or higher (QTcF >500 ms on at least two separate ECGs).
- An increase for QTcF with >60 ms change from baseline (Visit 2) or QTcF >500 ms at any ECG recording (triplicate mean or single) needs to be confirmed by an ECG recording as soon as possible from the original abnormal recording at the same visit. In case of an abnormal ECG on both of these two recordings, the investigator needs to send an immediate alert to the CRO medical monitor (as per study contact list) or sponsor's study physician (if the former is not available). If the ECG abnormality is before IMP intake, IMP administration will be withheld until the central reader has reviewed the ECG registration. In case of confirmation of the ECG abnormality, IMP will be discontinued for this subject.

- Increase in LFT:
  - AST or ALT  $\geq 8x$  ULN.

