  - AST or ALT  $\geq 3x$  ULN with signs of severe liver damage (i.e. with the appearance of fatigue, nausea, vomiting, right upper quadrant pain or tenderness, fever, rash and/or eosinophilia [ $>5\%$ ], and/or total bilirubin  $\geq 1.5x$  ULN or international normalized ratio [INR]  $>1.5$ ).
  - AST or ALT  $\geq 3x$  ULN for more than 2 weeks.
- Clinical laboratory test suggestive of cholestasis with total serum bile acid levels  $>3x$  ULN on a sample taken in fasted state (at least 8 hours fasted). If the routine random or postprandial total serum bile acid sample is  $>3x$  ULN, then the subject should have a fasted sample taken within 1 to 5 days. The results of this test will determine whether the subject should discontinue IMP or not.

When test results need to be confirmed, the subject should return to the clinical study center and be evaluated as soon as possible, preferably within 48 hours from awareness of the abnormal results. This evaluation should include laboratory tests, detailed history, and physical assessment. In addition to repeating AST and ALT, laboratory tests should include albumin, creatine kinase, total bilirubin, direct and indirect bilirubin, gamma glutamyl transferase (GGT), INR, and alkaline phosphatase. A detailed history, including relevant information, such as review of ethanol, recreational drug and supplement consumption, family history, sexual history, travel history, history of contact with a jaundiced subject, surgery, blood transfusion, history of liver or allergic disease, and work exposure, should be collected. Further testing for acute hepatitis A, B, or C infection and liver imaging (e.g. biliary tract) may be warranted. All cases confirmed on repeat testing with no other cause for LFT abnormalities identified at the time should be considered potential Hy's Law cases irrespective of availability of all the results of the investigations performed to determine etiology of the abnormal LFTs. Such potential Hy's Law cases should be reported as SAEs.

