### 3.3.4. Analysis Windows

All assessments including data collected on unscheduled visits, will be allocated to analysis visits (time windows) based on the relative day of the assessment (see section 3.3.1) and according to the algorithm in Table 2. TFLs will present the analysis visits when analysis is derived.

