#### 5.4.3.9. Presentation of Results

No formal inferential statistics (p-values) will be provided.

Continuous parameters will be summarized by means of descriptive statistics (including 95% CI of the mean change from t-test) by parameter, treatment group and analysis visit. Actual values and changes from baseline will be tabulated separately.

Figures of the mean ( $\pm$  SE) actual values over time and of the mean ( $\pm$  SE) change from baseline will be prepared for all parameters.

All laboratory abnormalities after the first dose of study medication up to 30 days after the last dose, if the subject did not enroll in the OLE study, or the earliest between the last IMP intake + 30 days during the double-blind study and the first dose of IMP in the OLE study (excluded), if the subject continues in OLE, will be included.

Abnormalities of the actual values will be presented as shift tables of the worst-case abnormality versus the baseline abnormality/toxicity grade. The table will be created per parameter and treatment group for the on-treatment analysis period. The results of non-graded abnormalities and toxicities grades will be shown separately.

---

A frequency table of the number (percentage) of subjects with treatment-emergent worst-case abnormalities per parameter and treatment group for the on-treatment analysis period will be presented. The results of non-graded abnormalities and toxicities grades will be shown separately.

Urinalysis tests for which no normal range is available will be tabulated separately as categorical data.

Clinical laboratory values will also be listed including normal ranges and indicating if value is out of range. Separate listings will also be created to include all laboratory values of a subject who has had at least one value meeting CTCAE grading 3 or higher category.

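### SAP 3.3.4 gives the planned value no priority in its window, so a repeat ordered because of an abnormal result can replace that result in by-visit laboratory and ECG summaries

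*SAP*

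**What the plan says.** **Allocation.** Under SAP 3.3.4, "All assessments including data collected on unscheduled visits, will be allocated to analysis visits (time windows) based on the relative day of the assessment".

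**Selection.** Under Selection of Visits, one value is kept per parameter, analysis visit and timepoint: "the value closest to the target date will be used in analysis tables and figures". For ties: "If more than one value is located at the same distance from the target day, then the latest in time will be selected". For untimed pairs: "If there are two values on the same day and no time indicating which one is last, the average of the two will be calculated". Values not selected are only listed. Nothing in the visible text prefers the planned record or sets aside a repeat that was triggered by that record's result.

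**Triggered repeats (Protocol 4.5.4).** A QTcF above 500 ms, or more than 60 ms above baseline, "needs to be confirmed by an ECG recording as soon as possible from the original abnormal recording at the same visit". For liver tests that need confirmation, the subject returns as soon as possible, preferably within 48 hours of awareness of the result. If a random or postprandial bile-acid value exceeds 3x ULN, "then the subject should have a fasted sample taken within 1 to 5 days".

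**Where the selected value is used.** SAP 5.4.3.9 (laboratory) and 5.4.4.4 (ECG) summarise actual values and changes by treatment group and analysis visit, with a 95% CI for the mean change. Laboratory data also get mean plots over time.

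**Where every record is used.** The worst-case derivations in SAP 5.4.3.7 and 5.4.4.3 take all on-treatment post-baseline records, including unscheduled ones. The shift and treatment-emergent tables are built on them. The hepatotoxicity table (5.4.3.8) counts any subject with at least one qualifying assessment.

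**The concern.** Under these protocol rules a normal result prompts no repeat, so nothing competes with it in its window. An abnormal result does prompt one, and the repeat competes on equal terms or, in a tie, on better terms. Which value reaches the by-visit summary can therefore depend on the outcome being summarised. If part of the abnormal value was noise, its repeat tends to lie closer to normal. Replacing only such values then pulls the by-visit mean towards normal, and more so in an arm where a larger share of subjects have triggered repeats.

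What is at stake is the accuracy of the by-visit means, CIs, minima and maxima for laboratory and ECG parameters, and of the laboratory mean plots, in a trial of about 20 and 10 subjects per arm.

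**Working it through.** The documents give no figure for this, so there is none to reproduce.

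**1. Same-visit ECG repeat.** The two recordings share a study day and so tie on distance from target. Three outcomes are possible for a pair at the same timepoint:
- With times recorded, the tie rule selects the repeat.
- Without times, the two values are averaged (Selection of Visits).
- If the pair counts as a duplicate, it is averaged under SAP 5.4.4.2, which averages triplicates or duplicates. This reading is open at Visits 7 and 9, where Protocol 6.6.5 plans a single ECG.

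The SAP does not say whether a confirmatory ECG is a duplicate.

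**2. Later-day laboratory repeat.** Let d be the visit's offset from the target day and r the lag of the repeat in days. The repeat is selected if |d + r| ≤ |d|, that is, if d ≤ -r/2. A visit on or after the target day therefore always keeps its value. Protocol 6.1 allows ±2 days for Visits 3 and 4 and ±4 days for later treatment visits; the extended COVID-19 window for Visit 9 is left aside. Counting offsets, with all days in the window assumed equally likely:

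| Lag r (days) | ±4-day window | ±2-day window |
|---|---|---|
| 1-2 | 4/9 | 2/5 |
| 3-4 | 3/9 | 1/5 |
| 5-6 | 2/9 | 0 |
| 7-8 | 1/9 | 0 |
| 9 or more | 0 | 0 |

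Example: a Week 24 sample on Day 168 and a repeat on Day 170 tie around Day 169, so Day 170 is used. Averaged over lags of 1 to 5 days, the bile-acid range, the ±4-day figure is (4+4+3+3+2)/45 = 16/45 = 36% and the ±2-day figure is (2+2+1+1+0)/25 = 6/25 = 24%.

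**3. Effect of one replaced subject.** The arm mean moves by (planned value - repeat)/n. With illustrative differences, not taken from the documents:
- a QTcF repeat 20 ms lower gives 20/20 = 1.0 ms (n=20) or 20/10 = 2.0 ms (n=10);
- an ALT repeat lower by 2x ULN gives 2/20 = 0.10x ULN or 2/10 = 0.20x ULN.

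**4. Expected pull if repeats regress to the mean.** Take a normally distributed value with an upper-tail trigger at cut-off c, test-retest correlation ρ and replacement probability P. In SD of a single value, the pull is (1 - ρ) × φ(c) × P. The trigger rates and ρ = 0.5 to 0.9 are assumptions.
- 20% triggered, φ(c) = 0.280. With P = 1: 0.5 × 0.280 = 0.14 down to 0.1 × 0.280 = 0.03. With P = 4/9: 0.06 down to 0.01.
- Between arms, 20% versus 5% triggered. With P = 1: 0.09 down to 0.02. With P = 4/9: 0.04 down to 0.01.

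A simulation with a true mean of 0, 20% triggered and ρ = 0.5 gave a mean of -0.139 SD when the repeat replaces the value and -0.069 SD when the two are averaged. Averaging halves the pull but does not remove it.

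**The case against.** Closest-to-target is a transparent, prespecified rule, and several stronger readings that a reader might infer do not follow from the documents.

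- **That an ECG repeat always replaces the planned value.** Both averaging rules stand in the way, and the pair competes only if it is held under the same timepoint. What is established is that replacement happens when times are recorded and the pair is not averaged.
- **That 44% is the laboratory figure.** It needs a repeat 1-2 days after sampling. The 48 hours for liver tests run from awareness, and Protocol 6.10 sends samples to a central laboratory, so longer lags and lower fractions are likely. Visits clustered on the target day would lower them further.
- **That the pull must be towards normal.** A sustained drug effect largely reproduces on repeat, and a rising value would be replaced by a higher one. The direction holds only so far as the repeats regress.
- **That repeats reflect a drug hold.** This is thinly supported. The ECG repeat is at the same visit, and the fasted bile-acid result is what determines discontinuation. It is plausible mainly for liver tests that already meet a stopping criterion.
- **That a threshold exceedance disappears.** The category above 60 ms in SAP Table 6 is counted worst-case from all records. SAP 5.4.4.4 plans no ECG mean plots that could be distorted.

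It is also fair that triggers may be rare. Screening QTcF above 450 ms is excluded, and Protocol 2.2.1 reports no clinically significant laboratory or ECG abnormalities in the completed studies it describes. Safety has no formal testing.

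These points limit the size and certainty of the effect. They do not remove the mechanism: nothing visible in the SAP prevents outcome-dependent selection, and the two ECG rules remain unreconciled.

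**Conclusion.** The point holds as a modest, cheap improvement. As written, SAP 3.3.4 lets a repeat ordered because of an abnormal result stand in for that result in the by-visit laboratory and ECG descriptive summaries and the laboratory mean plots. For a later-day laboratory repeat this requires a visit before the target day. For a same-visit ECG repeat it depends on which of the SAP's rules governs.

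The expected bias is small: about 0.01 to 0.14 SD within an arm at an assumed 20% trigger rate, and 0.01 to 0.09 SD between arms at 20% versus 5%. Both ranges rest on assumed test-retest correlations and, for laboratory data, on equally likely visit days and a lag of 1-2 days. A single subject can still be visible with about 20 and 10 per arm. What matters is the share of subjects with triggered repeats, since one placebo repeat weighs twice as much as one active repeat.

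A reader might infer that the plan hides a safety signal. It does not, because the abnormal value stays in the all-records tables and the listings. Part of the Table 2 footnote and SAP 5.4.3.1 cannot be read in the public text, so the conclusion rests on what is visible.

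**What to change.** Add to SAP 3.3.4, for by-visit laboratory and ECG summaries:
- The value from the planned visit takes precedence. If several planned values fall in one window, use the one closest to target.
- Unscheduled or confirmatory values are used only if the window holds no valid planned value.
- An early-discontinuation value need not override an unscheduled value much closer to target when the planned visit was missed. The ECG Week 2 window runs from Day 3 to Day 64, so blanket precedence could select a Day 60 early-discontinuation ECG over a Day 15 unscheduled one.

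Add to SAP 5.4.4.2 that a confirmatory ECG is not part of a planned triplicate or duplicate. Leave the worst-case, shift and treatment-emergent tables on all records.

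Where a planned value exists, the replacement probability becomes zero and so does the pull. The cost is a few lines of SAP text and a programming flag. The downside is that an occasional repeat nearer to the target day is listed instead of tabulated.

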## **3.4. HANDLING OF DATA**

### **3.4.1. Handling of Missing Data**

#### **3.4.1.1. Handling of Missing Date Time Data**

Generally no imputations will be done in case of missing date (time) fields, nor for the missing parts of partially known date (time) fields apart from partially missing initial diagnosis dates.

When the date of initial diagnosis is partially missing, the following rules will be used in order to determine the duration of disease:

- If the day of initial diagnosis is missing, then 01 will be assigned to the missing fields.
- If the month of initial diagnosis is missing, then January will be assigned to the missing fields.
- If date of initial diagnosis is completely missing, no imputation will be done.

Assessments with completely missing date (time) will be omitted from the analysis.

Event-type data (e.g. adverse events, concomitant medications) with missing date (time) will be allocated to analysis periods using a worst-case approach as explained in the respective sections.

#### **3.4.1.2. Handling of Missing Result Data**

No imputation will be done of missing results unless specified otherwise in corresponding sections (i.e. observed cases (OC) analysis).

### **3.4.2. Handling of Values Below or Above a Threshold**

Values below (above) the quantification limit will be imputed by the value one unit smaller (larger) than the quantification limit itself. In listings, the original value will be presented.

Example: if the database contains the value “<0.04”, then for the descriptive statistics the value “0.03” will be used. The value “>1000” will be imputed by “1001”.

---

### 3.4.3. Handling of Outliers

There will be no outlier detection, all measured values will be included in the analyses

## 3.5. PRESENTATION OF RESULTS

### 3.5.1. Presentation of Treatment groups

In the section Subject Information, a grand total “All Subjects” will be added to summarize all subjects over all treatment groups in tables.

### 3.5.2. Calculation of Descriptive Statistics

For continuous parameters, descriptive statistics will be presented when  $n \geq 2$ . When  $n=1$ , the summary statistics will be included in tables and figures. Only the summary statistics for  $n$  and mean will be displayed, other summary statistics will be left blank.

Descriptive statistics will include:

- the number of non-missing data points ( $n$ )
- the arithmetic mean
- the standard error (SE) and standard deviation (SD)
- the median, minimum and maximum
- 95% confidence interval (CI) of the mean (if indicated in the relevant section).

### 3.5.3. Calculation of Percentages

Frequencies and percentages will be generated for categorical parameters.

For event-type data (e.g. Adverse Events), the denominator will be all subjects in the analysis set and analysis visit/period. For other data (e.g. worst-case analysis of assessments), the denominator will be all subjects with post-baseline data for the parameter, in the analysis set and analysis visit/period.

### 3.5.4. Additional Considerations

All data collected except for assessment that were not done (and hence assessment date is missing) will be listed in data listings.

## 4. PRIMARY ANALYSIS AND FINAL ANALYSIS

There will be no interim analysis in the study. The primary analysis will be performed when all subjects have completed the Week 24 visit (or discontinued earlier), providing all tables, listings and figures based on the data collected and cleaned up to Week 24 visit. Every effort will be made to keep the subjects and investigators blinded to individual treatment assignments until completion of the final analysis (after the last subject has completed the last follow-up visit in CL-204 study). Upon the completion of the post-treatment period in the CL-204 study, the final analysis will be performed.

## 5. STATISTICAL ANALYSES

### 5.1. CHANGES TO THE PLANNED ANALYSES, NOT COVERED BY PROTOCOL AMENDMENTS

- All Enrolled Analysis Set will not be used for the analyses so not included in SAP.
- All Randomized Analysis Set will be used for the presentation and summary of the baseline assessments to better interpret the study data.
- Definition of Per-Protocol Analysis Set was slightly modified within this SAP text as unblinding will occur at the time of primary analysis, i.e. not at the same time of database lock.
- Definition of Per-Protocol Analysis Set was modified to exclude subjects who had mRSS assessment at Week 24 outside of the original time window of [142, 183] study day.

- An additional sensitivity analysis for the primary endpoint was added where for subjects that did not have a Week 24 mRSS assessment at all within the extended window, but possibly in the Week 28 - Week 32 interval, their Week 28 result will be allocated to Week 24 analysis visit.

---

## 5.2. SUBJECT INFORMATION

Subject information will be tabulated using the FAS unless otherwise specified. No inferential testing will be performed, nor will p-values be provided.

Subject information will be tabulated with descriptive statistics per treatment group and overall.

### 5.2.1. Demographic and Baseline Disease Characteristics

The following parameters will be summarized:

- Gender: Male; Female
- Age at signing the ICF (years)
- Age, categorized (years): age  $\leq$  45; age  $>$  45
- Ethnicity: Not Reported; Hispanic or Latino; Non Hispanic or Latino; Unknown
- Race: American Indian or Alaskan Native; Asian; Black or African American; Native Hawaiian or Other Pacific Islander; and White
- Is the Subject of Japanese Ancestry?: Yes; No
- Baseline Height (cm)
- Baseline Weight (kg)
- Body Mass Index BMI (kg/m^2)

Age, height, weight, and BMI will be summarized using descriptive statistics. The number and percentage of subjects by age category, gender, ethnicity, and race will also be reported.

A summary of baseline information will be presented and summarize the following parameters:

- Duration of disease (years) =  $\frac{(\text{date of first IMP intake}) - (\text{date of initial diagnosis}) + 1}{365.25}$
- Duration of disease, categorized (years): duration  $<$  2; duration  $\geq$  2
- Baseline total mRSS scores

Subjects with/without lung disease at baseline: presence of lung disease at baseline is defined based on Scleroderma Clinical Trials Consortium (SCTC) criteria identified based on medical history data. Subjects with lung disease at baseline will be defined as subjects with any medical history preferred term of 'Interstitial lung disease' or 'Systemic sclerosis pulmonary'

---

that were active at baseline (i.e. start date is prior to first dose of study medication and end date is after first dose of study medication or ongoing). All other baseline efficacy and safety parameters will be presented together with post-baseline results by timepoint tables.

For more details on the imputation of date of initial diagnosis, refer to section [3.4.1.1](#).

